2.3.1. Risk Assessment

Potential Risk of Clinical Significance	Summary of Data/Rationale for Risk	Mitigation Strategy
Study Intervention(s): PF-07321332		
Emesis	
Sporadic emesis were observed at ≥ 100 mg/kg/day of PF-07321332 in the 15-day NHP toxicology study (See IB). Based on preliminary data, no emesis was observed in the FIH study C4671001 at single doses of PF-07321332 up to 1500 mg alone and up to 750 mg administered with ritonavir (100 mg at -12h, 0h, 12h), and at repeated daily doses administered orally for 10 days of up to 500 mg PF-07321332 BID with 100 mg ritonavir BID.
	
As this is an investigational agent, there is some risk that is mitigated by close observation of AEs, etc. If needed, palliative care or antiemetics may be provided.

Neuronal and pulmonary effects	
Transient effect in rat neuronal and pulmonary endpoints were observed in rat toxicology study at the high dose level (1000 mg/kg as single dose; See IB). Based on preliminary data, no AEs suggestive of neuronal or pulmonary effects were observed in the FIH study C4671001 at single doses of PF-07321332 up to 1500 mg alone and up to 750 mg administered with ritonavir (100 mg at -12h, 0h, 12h), and at repeated daily doses administered orally for 10 days of up to 500 mg PF-07321332 BID with 100 mg ritonavir BID.
	
Vital signs, including respiratory rate, will be monitored for pulmonary effect. There will be close observation of AEs for any signs of neuronal effect.

Hemodynamic effects	
Low level inflammation (increase in fibrinogen) in 15-day NHP toxicology study and changes in platelets, globulin and albumin/globulin ratio and coagulation system (increase in PT and aPTT) in 14-day rat toxicology study (See IB). No relevant laboratory changes in inflammatory markers have been observed in the FIH study C4671001 at single doses of PF-07321332 up to 1500 mg alone and up to 750 mg administered with ritonavir (100 mg at -12h, 0h, 12h), and at repeated daily doses administered orally for 10 days of up to 500 mg PF-07321332 BID with 100 mg ritonavir BID.
	
Fibrinogen, platelets, PT and aPTT, albumin and total proteins will be monitored.

Potential Risk of Clinical Significance	Summary of Data/Rationale for Risk	Mitigation Strategy
Thyroid function studies	In 14 day rat toxicology study at high dose of PF-07321332 (1000 mg/kg/day) thyroid gland changes observed were of low severity and without evidence of tissue damage. In the FIH study C4671001, 3 participants had TEAEs of elevated TSH levels across treatment groups (PF-07321332 or placebo with ritonavir 100 mg BID) in the MAD part of the study. There was no clinical correlation with these TSH changes and free T4 remained within reference range at all times.	TSH and free T4 will be evaluated to monitor thyroid function
Study Intervention(s): Ritonavir		
Gastrointestinal disturbances (including diarrhea, nausea, vomiting and abdominal pain).	Frequently reported adverse reaction in HIV patients at 600 mg BID.	Lower dose of 100 mg twice daily is used in this study. There will be close observation of AEs. If needed, anti-emetics may be provided.
Neurological disturbances (eg, paresthesia, including oral paresthesia, dysgeusia and dizziness).	Frequently reported adverse reaction in HIV patients at 600 mg BID.	Lower dose used in this study. There will be close observation of AEs.
Rash (most commonly reported as erythematous and maculopapular, followed by pruritic).	Frequently reported adverse reaction in HIV patients at 600 mg BID.	Lower dose used in this study. There will be close observation of AEs and monitoring through targeted physical exams. If needed, palliative care may be provided.
Fatigue/Asthenia	Frequently reported adverse reaction in HIV patients at 600 mg BID.	Lower dose used in this study. There will be close observation of AEs and monitoring through targeted physical exams.
Limited case reports of renal toxicity	Although ritonavir therapy is not generally considered nephrotoxic, a limited number of cases of acute kidney injury secondary to ritonavir have been reported post-marketing in HIV patients.	Lower dose used in this study. There will be close observation of AEs and renal function.

2.3.2. Benefit Assessment

PF-07321332/ritonavir will not provide any clinical benefit to healthy participants or participants with renal impairment in this study. Any anticipated benefit to participants would be in terms of contribution to the process of developing a new therapy in an area of unmet medical need.

2.3.3. Overall Benefit/Risk Conclusion

Taking into account the measures to minimize risk to study participants, the potential risks identified in association with PF-07321332/ritonavir are justified by the anticipated benefits that may be afforded to participants with COVID-19.

3. OBJECTIVES AND ENDPOINTS

Objectives	Endpoints
Primary:	Primary:

Part 1: To evaluate the effect of mild (if applicable) and moderate renal impairment on the PK of PF-07321332, following a single oral dose administration of PF-07321332 pharmacokinetically boosted with ritonavir.Part 2: To evaluate the effect of severe renal impairment on the PK of PF-07321332, following a single oral dose administration of PF-07321332 pharmacokinetically boosted with ritonavir.	
Plasma PF-07321332 PK parameters: C_{max}, AUC_{inf} (or AUC_{last} if AUC_{inf} cannot be reliably estimated)Urine PF-07321332 PK parameters: A_e, CL_r, if applicable and as data permit
Secondary:	Secondary:

To evaluate the safety and tolerability of PF-07321332 and ritonavir, following a single oral dose administration of PF-07321332 pharmacokinetically boosted with ritonavir, in participants with renal impairment and in healthy participants with normal renal function.To characterize additional PK parameters of PF-07321332 following a single oral dose of PF-07321332 pharmacokinetically boosted with ritonavir by renal function.	
Safety: treatment-emergent adverse events, clinical laboratory tests, vital signs, physical examination and ECGs.Plasma PF-07321332 PK parameters: C_{12}, C_{24}, T_{max}, AUC_{last}, CL/F, V_z/F, and $t_{1/2}$, as data permit.

4. STUDY DESIGN

4.1. Overall Design

This is a Phase 1, non-randomized, open-label, 2-part study to investigate the effect of renal impairment on the plasma and urine (if applicable) PK, safety and tolerability of a single oral dose of PF-07321332 in combination with the PK boosting agent ritonavir in approximately

36 participants. Part 1 will be conducted in approximately 24 adult male and female participants with stable mild or moderate renal impairment and a control group of participants with normal renal function. Part 2 will be conducted in approximately 8 adult male and female participants with stable severe renal impairment. A staged approach, as outlined in detail below, will be followed in the study.

Participants will be selected and categorized into normal renal function or renal impairment groups based on their eGFR as shown in Table 1.

Table 1. Renal Function Categories by eGFR Ranges

Cohort	Renal Impairment ^a	Estimated eGFR ^b (mL/min)	Number of Participants
1	Moderate Renal Impairment	≥30 to <60	8
2	Mild Renal Impairment	60 – <90	8
3	None (Normal)	≥90	8 (up to 12)
4	Severe Renal Impairment	<30 and not requiring dialysis	8

- a. Stages of renal impairment are based on Kidney Disease Outcomes Quality Initiative (KDOQI) Clinical Practice Guidelines for Chronic Kidney Disease (CKD).⁵
- b. Estimate of eGFR based on CKD-EPI formula. The average of the 2 screening eGFR value will be used for group assignment.

Part 1: Approximately 24 participants will be enrolled in Part 1; approximately 8 participants with moderate renal impairment (Cohort 1), approximately 8 with mild renal impairment (Cohort 2), and approximately 8 (up to 12) with normal renal function (Cohort 3), to ensure at least 6 evaluable participants in each group. Participants from the moderate renal impairment group (Cohort 1) will be recruited first. Enrollment into Cohort 2 will initiate, if necessary (see criteria below), after preliminary analysis of PK and safety data from at least 2 participants with moderate renal impairment have been reviewed. The healthy participants (Cohort 3) will be recruited later such that each participant's age is within ±10 years and weight is within ±15 kg of the mean of participants within the renal impairment groups. An attempt will be made to maintain a similar male/female ratio composition between groups. Care will be taken when recruiting the healthy participants such that the entire group is not of substantially different age or of substantially different body weight than the moderate renally impaired participants. Approval from the sponsor must be obtained before proceeding with dosing healthy participants with normal renal function.

Participants with stable mild and moderate renal impairment and control participants with normal renal function will receive a single 100 mg dose of PF-07321332 administered orally in combination with the PK boosting agent ritonavir administered as a 100 mg dose at -12, 0, 12, and 24 hours relative to PF-07321332 dosing. Blood and urine samples will be collected for measurement of plasma and urine concentrations of PF-07321332 as per SoA.

If there are participants who withdraw or discontinue treatment from the normal or mild or moderate renal impairment groups and who are considered to be non-evaluable with respect to the primary PK objective, additional participants can be enrolled at the discretion of the sponsor.

Criteria to enroll Cohort 2: After preliminary evaluation of results from participants with moderate renal impairment (Cohort 1), enrollment of participants with mild renal impairment (Cohort 2) may be initiated. Cohort 2 will be conducted if the estimate of the ratio of PF-07321332 AUC_{inf} for the moderate renal impairment group compared to healthy normals is ≥ 1.5 .

Part 2: The decision to conduct Part 2 will be made based on results from Part 1. Enrollment into Part 2 will not commence until preliminary analysis of PK and safety data from at least 2 participants with moderate renal impairment have been reviewed. Approximately 8 participants with severe (Cohort 4) renal impairment will be enrolled to ensure at least 6 evaluable participants in each group. As in Part 1, renal impairment classification will be based on eGFR. Participants will receive a single 100 mg dose of PF-07321332 administered orally in combination with the PK boosting agent ritonavir administered as a 100 mg dose at -12, 0, 12, and 24 hours relative to PF-07321332 dosing. Blood and urine samples will be collected for measurement of plasma and urine concentrations of PF-07321332 as per [SoA](#). Healthy participants from Part 1 will be used as the control group for the severe impairment participants. If necessary, additional participants may be enrolled into the normal renal function group to ensure adequate matching; however the total number will not exceed 12.

The dose of PF-07321332 may be reduced for participants with severe renal disease if considered necessary by the investigator and sponsor to ensure participant safety. Similarly, the timings of sample collection may be adjusted during study conduct on the basis of emerging data in order to allow optimal characterization of the PK profile, eg, additional post-dose sample collection may be introduced, etc.

When recruiting the Part 2 participants, attempts to match the entire group to the participants in Part 1 with respect to age, gender and body weight will be made. Other demographics, such as race and ethnicity, may be considered for matching the Part 1 and Part 2 populations when possible. Statistical considerations to account for any differences in demographics are detailed in [Section 9.3](#).

As in Part 1, if there are participants who withdraw or discontinue treatment from the severe impairment group and who are considered to be non-evaluable with respect to the primary PK objective, additional participants can be enrolled at the discretion of the sponsor.

For both Parts 1 and 2: All participants in both normal and renal impairment groups will provide informed consent and undergo Screening evaluations to determine their eligibility. Participant screening for participation in this study will consist of 2 CRU outpatient visits not more than 14 days apart (but at least 3 days apart), with the first screening visit occurring within 28 days prior to administration of investigational product. An eGFR value for group placement (provided stable renal function is still demonstrated) will be obtained by the average of the 2 screening values (using the CKD-EPI equation). If the renal function stability criterion is met but the renal function classification category changes between S1 eGFR and the average of the S1 and S2 eGFRs, the eGFR measurement at Day -1 will also be used to determine the appropriate group classification category using an average of all 3 GFR values, to determine whether the participant will be eligible for enrollment.

Eligible participants will be admitted to the CRU on Day -1 (at least 12 hours prior to the dosing of PF-07321332 on Day 1) and will be confined in the CRU until Day 3. If participant meets all screening criteria at S2 visit, and Day -1 visit can be performed immediately, the participant may be admitted to the unit at conclusion of S2 visit.

On the evening of Day -1, participants will receive a single 100 mg dose of ritonavir (-12 hr relative to PF-07321332 on Day 1). On the morning of Day 1, the participants will receive a 100 mg single dose of PF-07321332 with a 100 mg dose of ritonavir after a fast of at least 10 hours. No food will be allowed for at least 4 hours post-dose. Ritonavir, 100 mg, will continue to be dosed at 12 and 24 hours post PF-07321332 dosing to ensure maintenance of the PK boosting effect. Serial blood and urine samples at specified intervals (as per [SoA](#)) will be collected for 48 hours post-dose for plasma and urine PK assessments, prior to discharge from the CRU on Day 3. The eGFR value determined on Day -1 will be used for PK analysis.

Safety assessments (as specified in the [SoA](#)) will be performed during S1, on Day -1 prior to dosing, Day 1, and on Day 3. Only serum creatinine will be additionally assessed on S2 for eGFR estimation. Physical examinations, vital sign measurements, and clinical laboratory tests will be conducted and AEs will be monitored as per [SoA](#) to assess safety. The total participation time (ie, CRU confinement time for study procedures) for each participant in this study is approximately 3 nights/4 days (excluding screening & Follow-Up contact). Participants will have a follow-up phone contact 28-35 days after last- ritonavir administration or from the time of early termination/discontinuation to assess for AEs. If participant demonstrates an increase of >25% in SCr from Day -1 to Day of discharge, he or she will be asked for a follow-up visit to collect eGFR. The total planned duration of participation, from the Screening visit to the last Follow-up phone call, is approximately up to 9 weeks.

All procedures and their timelines follow the [SoA](#).

Calculation of eGFR:

The following CKD-EPI equation will be used to calculate eGFR ($S_{Cr, std}$ denotes serum creatinine measured with a standardized assay for serum creatinine):

If female and SCr is ≤ 0.7 mg/dL:

$$eGFR \text{ (mL/min/1.73 m}^2\text{)} = 144 \times (S_{Cr, std}/0.7)^{-0.329} \times 0.993^{\text{age}} \times 1.159, \text{ if Black}$$

If female and SCr is > 0.7 mg/dL:

$$eGFR \text{ (mL/min/1.73 m}^2\text{)} = 144 \times (S_{Cr, std}/0.7)^{-1.209} \times 0.993^{\text{age}} \times 1.159, \text{ if Black}$$

If male and SCr is ≤ 0.9 mg/dL:

$$eGFR \text{ (mL/min/1.73 m}^2\text{)} = 141 \times (S_{Cr, std}/0.9)^{-0.411} \times 0.993^{\text{age}} \times 1.159, \text{ if Black}$$

If male and SCr is >0.9 mg/dL:

$$\text{GFR (mL/min/1.73 m}^2\text{)} = 141 \times (\text{S}_{\text{Cr, std}} / 0.9)^{-1.209} \times 0.993^{\text{age}} (\times 1.159, \text{ if Black})$$

Note that the value of eGFR, which is directly obtained from the laboratory or calculated using the equation above, is generally normalized to an average body size of 1.73 m² for diagnosis, prognosis and treatment of renal disease. In terms of clearance of renally filtered drugs (including secreted drugs), renal elimination capacity is related to absolute GFR in mL/min. To use the CKD-EPI-derived, BSA-adjusted value of eGFR to obtain absolute GFR (mL/min) for renal disease classification or participant assignment into different renal disease groups, this value should be multiplied by the individual participant's BSA (ie, measured BSA/1.73 m²). The BSA of an individual can be calculated by the following formula as described below:

$$\text{BSA} = (\text{Weight}^{0.425} \times \text{Height}^{0.725}) \times 0.007184$$

In summary, GFR in mL/min calculated as below will be used for renal impairment group placement:

Step 1: Obtain the CKD-EPI-derived eGFR:

Step 2: Convert the CKD-EPI-derived, BSA-adjusted eGFR obtained above to absolute GFR (mL/min) for eligibility assessment using the following equation:

- eGFR (mL/min) = eGFR (mL/min/1.73m²) × participant's BSA, where BSA is calculated as $\text{BSA} = (\text{Weight}^{0.425} \times \text{Height}^{0.725}) \times 0.007184$.

CL_{CR} will also be estimated from a spot serum creatinine measurement using the following C-G equation:

$$\text{CL}_{\text{CR}} (\text{mL/min}) = \frac{(\text{140} - \text{age [years]}) \times \text{total body weight (kg)} \times (0.85 \text{ for females})}{72 \times \text{serum creatinine (mg/dL)}}$$

Note that eGFR calculated by the CKD-EPI equation will be used for categorization of degrees of renal impairment. Nevertheless, renal function will be estimated using both C-G and CKD-EPI equations in this study and dose recommendations will be made using both C-G and CKD-EPI equations.

To be enrolled into the study, participant must demonstrate stable renal function, with $\leq 25\%$ change based upon screening S1 eGFR and screening S2 eGFR (calculated by the CKD-EPI equation). The S2 eGFR assessment should be performed between 3 to 14 days

after the S1 eGFR assessment. The average of these 2 eGFR values will be used for group placement based on the renal function classification category.

- If the renal function stability criterion is met and the renal function classification category remains the same between S1 eGFR and the average of the S1 and S2 eGFRs, participant will be eligible for enrollment.
- If the renal function stability criterion is not met, participant will be screen failed.
- If the renal function stability criterion is met but the renal function classification category changes between S1 eGFR and the average of the S1 and S2 eGFRs, the eGFR measurement at Day -1 will also be used to determine the appropriate group classification category using an average of all 3 eGFR values, to determine whether the participant will be eligible for enrollment.

In case of screen failure related to eGFR stability and/or change in the renal function classification category, participant may be re-screened once after a 30-day period, provided that the initial screen failure is not due to an Inclusion/Exclusion criterion that results in permanent disqualification from enrollment (eg, medical history). This can be done only with sponsor's approval.

Please see Table 2 below regarding demonstration of stable renal function:

Table 2. Criteria to Establish Stable Renal Function

Renal function Measurement	eGFR (mL/min)	Criterion for stability
S1	G1	N/A
S2 (Within 3 to 14 days after S1)	G2	$\Delta = G2 - G1 \times 100 / G1^a$ If $\Delta \leq 25\%$; stable If $\Delta > 25\%$; not stable

a. Parenthesis of || represents absolute values.

Serum creatinine laboratory test may be repeated once to confirm results at the discretion of the investigator; the last value will be used to calculate eGFR.

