2.1. Study Rationale

In vitro and in vivo metabolite profiling suggests that the primary clearance mechanism for PF-07321332 is CYP3A4 mediated oxidation. In a reaction phenotyping study using human liver microsomes in the presence of selective CYP inhibitors, CYP3A4 was predicted to be the major contributor ($f_m = 0.99$) to the in vitro oxidative metabolism of PF-07321332. As such, in the FIH study, C4671001, the CYP3A4 inhibitor ritonavir was used to enhance the exposure of PF-07321332 in order to achieve plasma levels that are anticipated to be efficacious. Preliminary PK data following multiple oral administrations of PF-07321332/ritonavir at doses of 75/100 mg, 250/100 mg, and 500/100 mg q12h suggest that the renal pathway may play a significant role in PF-07321332 excretion when co-administered with ritonavir, with approximately 32.5% (PF-07321332/ritonavir 500/100 mg) to 64.6% (PF-07321332/ritonavir 75/100 mg) of the drug excreted unchanged in urine across doses at steady-state, and renal clearance ranging between 3.5 to 4.4 L/h across doses.

PF-07321332/ritonavir is intended for short term (eg, 5 day) use, in patients with COVID-19, some of whom may have some degree of impaired renal function. Therefore, the purpose of this study is to characterize the effect of renal impairment on the plasma PK of PF-07321332/ritonavir. Findings from this study will be used to develop dosing recommendations so that the dose and/or dosing interval may be adjusted appropriately in the presence of renal disease.

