4.3. Justification for Dose

A single oral dose of 100 mg PF-07321332, pharmacokinetically enhanced with ritonavir (100 mg at -12, 0, 12, and 24 hours relative to PF-07321332), is planned in this study. This is anticipated to be at the lower end of the clinically effective dose range, and below the anticipated Phase 2/3 dose of PF-07321332/ritonavir of 300/100 mg. Although single doses up to 750 mg PF-07321332 with ritonavir have been evaluated, exposure increased less than dose proportional within the 250 mg to 750 mg dose range evaluated. Therefore, 100 mg PF-07321332 is appropriate considering systemic exposures of PF-07321332 may be increased in the presence of renal impairment.

When co-administered with ritonavir, doses of PF-07321332 up to 750 mg single dose and 500 mg q12h for 10 days were generally safe and well tolerated based on preliminary data

form the Phase 1 study C4671001. There have been no deaths or serious adverse events or SUSARs reported. Based on review of preliminary (unaudited) data, all reported adverse events have been of mild intensity. There were no clinically meaningful findings in vital signs, ECG, or potential Hy's Law cases reported during the study.

Doses may be modified in Part 2 based on emerging safety, tolerability, and PK data.

The dose of ritonavir to be used in this study is 100 mg administered q12h. This dose is the typical dose of ritonavir when dosed as a PK enhancer. As ritonavir is not eliminated renally, and is not expected to be significantly altered by renal impairment, no dose reduction is considered necessary.

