6.5. Dose Modification

Dose modifications for PF-07321332 and ritonavir are not allowed in Part 1. The dose of PF-07321332 may be reduced in Part 2 for participants with severe renal disease if considered necessary by the investigator and sponsor to ensure participant safety.

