8. STATISTICAL METHODOLOGY AND STATISTICAL ANALYSES

8.1. Statistical Methods

8.2. Statistical Analyses

ANOVA will be used to compare the natural log transformed AUC_{inf} (or AUC_{last} if AUC_{inf} cannot be reliably estimated) and C_{max} for PF-07321332 between normal renal function group (Reference) and each impaired renal function group separately as applicable (Test). Estimates of the adjusted mean differences (Test-Reference) and corresponding 90% CIs will be obtained from the model. The adjusted mean differences and 90% CIs for the differences will be exponentiated to provide estimates of the ratio of the adjusted geometric means (Test/Reference) and 90% CIs for the ratios. If substantial differences in demographic characteristics between healthy and impaired participants are observed, weight and age may be explored as covariates.

Box and whisker plots for individual participant parameters (AUC_{inf} and C_{max}) will be constructed by renal function group and overlaid with geometric means.

For summary statistics and median/mean plots by sampling time, the nominal PK sampling time will be used. For individual participant plots by time, the actual PK sampling time will be used.

Linear regression will be used to analyze the potential relationship between appropriate PK parameters (CL/F or CL_r , and V_z/F) and renal function (eGFR). Estimates of the slope and, intercept, together with their precision (90% CI), and the coefficient of determination will be obtained from the model.

Plots of PK parameters (CL/F or CL_r , and V_z/F) versus renal function (eGFR) will be constructed. A regression line and 90% confidence region for the PK parameters and eGFR will be included if appropriate. Vertical lines for the renal function group cut-off values will also be presented on the plots. Different symbols will be used to identify participants from different renal function groups.

Residuals from the model will be examined for normality and the presence of outliers via visual inspection of plots of residuals vs predicted values and normal probability plots of residuals but these will not be included in the clinical study report. If there are major deviations from normality or outliers then the effect of these on the conclusions will be investigated through alternative transformations and/or analyses excluding outliers. Justification for any alternative to the planned analysis will be given in the report of the study.

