10. APPENDICES

Appendix 1. SAS CODE FOR ANALYSES

- An example of the PROC Mixed code is provided below for ANOVA:

```
proc mixed data = tab.pk covtest alpha=0.1;
  class group;
  model l&var = group / S covb alpha=0.1 CL DDFM=KR;
  repeated/type=un subject=subjid group=group R;
  lsmeans group;
  estimate 'Moderate vs Normal'      group 1 0 -1 0;
  estimate 'Mild vs Normal'         group 0 1 -1 0;
  estimate 'Severe vs Normal'       group 0 0 -1 1;
  ods output lsmeans = lsmeans&var;
  ods output solutionf = solution&var;
run;

/* Letter assignments for group within the estimate statement above are as follows;

A = Moderate (Test);
B = Mild (Test);
C = Normal (Reference);
D = Severe (Test) */;
```

- Linear Regression Example code (Relationship between PK parameters (CL/F or CL_r and V_z/F) and renal function (eGFR):

```
Proc glm data=tab.pk
  class trt;
  model &var= trt &var1/ solution clparm alpha=0.1;
  ods 'FitStatistics' out=Rsq&var;
  ods 'Modelanova' out=tst&var;
  ods 'Parameterestimates' out=pe&var;
run;
```

Notes:

&var = [CL/F or CL_r] / V_z/F
&var1 = eGFR

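### If the permitted PF-07321332 dose reduction is used in the severe cohort, the primary severe/normal AUC and Cmax ratios are biased downward, because the ANOVA neither dose-normalises nor has a dose term

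*Protocol*

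**What the plan says.** Three protocol sections allow a different PF-07321332 dose in Part 2. Section 4.1 says "The dose of PF-07321332 may be reduced for participants with severe renal disease if considered necessary by the investigator and sponsor", Section 4.3 says "Doses may be modified in Part 2 based on emerging safety, tolerability, and PK data", and Section 6.5 repeats the permission for severe renal disease. No amount or number of participants is given.

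The reference group cannot follow. Section 4.1 states "Healthy participants from Part 1 will be used as the control group for the severe impairment participants", and Section 6.5 states "Dose modifications for PF-07321332 and ritonavir are not allowed in Part 1".

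On the analysis, SAP 8.2 begins "ANOVA will be used to compare the natural log transformed AUC" and applies the same model to Cmax, each impaired group against normal; protocol 9.3 agrees. The SAS statement in SAP Appendix 1 is "model l&var = group / S covb alpha=0.1 CL DDFM=KR", so renal group is the only term. SAP 6.4 lists no covariates, and SAP 8.2 allows only weight and age to be explored. Neither protocol Table 3 nor SAP Table 3 contains a dose-normalised AUC, Cmax, C12 or C24. SAP 2.1 describes 100 mg for every participant, including Cohort 4.

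**The concern.** The severe/normal ratio is the primary result of Part 2 and is meant to inform dosing recommendations. It answers the renal question only if both groups received the same dose, or if the analysis accounts for the difference. In the branch the protocol expressly permits, neither holds: the numerator would come from a lower dose and the denominator from 100 mg. The ratio would then understate the exposure increase in the most impaired group. If only some severe participants were reduced, that group's variance would also be inflated by the mixture of doses, and the SAS code estimates a separate variance per group.

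Other SAP provisions do not correct this. As-treated reporting (5.5) does not change the ratio. The rule on known biased estimates (7.3) removes participants, and applied to a whole reduced cohort it would leave no severe result. Section 8.3.3 only tabulates reductions due to adverse events. The clause on alternative analyses in 8.2 concerns non-normality and outliers.

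The 1.5 criterion for opening Cohort 2 and for assaying urine is unaffected: it compares moderate with normal, and Part 1 doses are fixed.

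**Working it through.** The documents give no power, variability or expected effect for this comparison, so there is no planned figure to reproduce. The check is how far the stated analysis moves once a reduction occurs.

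**Model.** Let f be the fraction of 100 mg given, b the exponent linking exposure to dose (b = 1 is proportional), and k of n severe participants reduced. On the log scale each reduced participant shifts by b·ln f, so

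reported ratio = true same-dose ratio × f^(b·k/n).

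For any f < 1 and b > 0 the multiplier is below 1, so the direction does not depend on the assumed values.

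**Range for b.** Protocol 4.3 says "exposure increased less than dose proportional within the 250 mg to 750 mg dose range evaluated"; nothing is stated at or below 100 mg. Protocol 2.1 gives 64.6% of the dose excreted unchanged at 75 mg and 32.5% at 500 mg, with "renal clearance ranging between 3.5 to 4.4 L/h across doses". Since AUC = fraction excreted × dose / CLr:

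- AUC500/AUC75 = (0.325 × 500)/(0.646 × 75) × CLr75/CLr500 = 3.354 × CLr75/CLr500.
- CLr is not given by dose, so its ratio lies between 3.5/4.4 = 0.795 and 4.4/3.5 = 1.257. The AUC ratio is then 2.67 to 4.22.
- b = ln(AUC ratio)/ln(500/75) = 0.517 to 0.759, or 0.638 if CLr is equal.

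These are steady-state data at 75 and 500 mg. They serve only as an illustrative range for AUC and give nothing for Cmax.

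**Reported ratio when the true ratio is 2.0.** The true ratio, f and k are assumptions; the f values are not proposed doses.

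| Reduced | f | b = 1 | b = 0.76 | b = 0.52 |
|---|---|---|---|---|
| 8 of 8 | 0.50 | 1.00 | 1.18 | 1.40 |
| 4 of 8 | 0.50 | 1.41 | 1.54 | 1.67 |
| 8 of 8 | 0.75 | 1.50 | 1.61 | 1.72 |

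For example, 2.0 × 0.5^0.517 = 2.0 × 0.699 = 1.40.

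**Coverage of the nominal 90% CI.** Simulation of 40,000 trials per setting: 8 versus 8, lognormal, unequal-variance interval, assumed CV 30%, 40% and 50%, true ratio 2.0, f = 0.5, whole cohort reduced. Coverage is about 0–13% at b = 1 and about 25–58% at b = 0.52.

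**Variance with partial use.** At CV 30% the log SD is √ln(1.09) = 0.29. Halving the dose in 4 of 8 at b = 1 adds (ln 2)²/4 × 8/7 = 0.137 to the variance, giving √(0.086 + 0.137) = 0.47.

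**Effect of simple normalisation.** Dividing by dose leaves a factor f^(b−1) when all are reduced. At f = 0.5 the estimate becomes:

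- 2.00 at b = 1, coverage about 90%;
- 2.0 × 0.5^(−0.241) = 2.36 at b = 0.76, coverage about 71–83%;
- 2.0 × 0.5^(−0.483) = 2.80 at b = 0.52, coverage about 31–62%.

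**A dose term instead.** If the whole severe cohort receives one reduced dose, the design matrix [intercept, group, log dose] has rank 2 of 3: dose is aliased with group and cannot be estimated. It is estimable only if some severe participants stay at 100 mg.

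**The case against.** The strongest reply is that the situation may never arise. The plan is 100 mg for all, Part 2 itself is optional, and a reduction is for safety only. 100 mg is already below the anticipated 300 mg, and single doses up to 750 mg with ritonavir were generally well tolerated. Only 100 mg tablets are supplied, to be swallowed whole, so the protocol would probably have to change before a reduction could be carried out, and an analysis rule could be added then. This limits how likely the problem is. It does not change what the analysis does in a branch that three sections allow. Adding the rule later would also mean changing the primary response variable in an open-label study with ongoing sponsor data reviews.

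Second, CL/F already carries dose and is summarised by cohort with geometric mean and CV (SAP Table 5). With CL/F = dose/AUCinf, the normal/severe ratio of geometric means equals the dose-normalised AUCinf ratio. That is right, and it means a careful reader would have a cross-check for AUCinf. But it leaves the primary ANOVA ratio uncorrected and does not cover Cmax. Protocol Table 3 also writes CL/F as AUCinf divided by dose, the inverse of clearance.

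Third, the sizes rest on assumed values, and at b = 0.52 normalisation does almost no better than the raw analysis: 2.80 against 1.40 for a true 2.0, with similar coverage. Both points stand. They are the reason normalisation needs a sensitivity analysis alongside it.

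**Conclusion.** The concern holds, conditionally. If the dose reduction allowed in Part 2 is used and the analysis is run as written, the primary severe/normal ratios for AUC and Cmax are biased downward, by f^b for a uniform reduction and f^(b·k/n) for a partial one. The factor equals f itself only under dose proportionality with the whole cohort at one dose. With f = 0.5 and a true ratio of 2.0, the reported AUC ratio would be 1.00 to 1.40 over b from 1 to 0.52.

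The direction is certain for any reduction with exposure rising with dose. The size is not, because f, k, b, the CV and the true ratio are all assumptions. With no reduction there is no bias. The point should be addressed before Part 2 data are analysed; confidence in its practical weight is medium because the trigger is optional.

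**What to change.** Add one conditional rule to protocol 9.3 and to SAP 8.2 and Table 3:

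- If any participant receives a PF-07321332 dose other than 100 mg, the severe-versus-normal ANOVA for AUCinf, AUClast and Cmax uses values normalised to 100 mg.
- C12 and C24 summaries are normalised in the same way. Unadjusted values are shown descriptively with the dose given.
- The dose-proportionality assumption is stated. A sensitivity analysis scales values by (100/dose)^b for b from about 0.5 to 1 and reports the ratio and 90% CI at each b.

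A dose covariate should not replace this, because of the aliasing shown above. The CL/F formula in protocol Table 3 should be corrected so that it can serve as a cross-check.

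Separately, the dose passages in protocol 4.1, 4.3 and 6.5, the tablet supply and administration instructions in 6.1 and 6.1.1, and the SAP's fixed 100 mg must be reconciled. No view is taken on which is right.

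The cost is one SAP paragraph with the matching protocol text, one derived variable and a short table, all dormant if no dose changes. The drawback is that normalisation over-corrects when exposure is less than proportional. At f = 0.5 in the whole cohort, moving b from 0.5 to 1 changes the adjusted ratio by 0.5^(−0.5) = 1.41, so after a reduction the severe/normal result would be reported as a range rather than as a single number.
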